#### 7.8.2.4 AEs of special interest (AESIs)

The protocol defines the following adverse event as AESI:

- **Hepatic injury**: A hepatic injury is defined by alterations of the hepatic laboratory and clinical parameters after randomisation as detailed by the removal and stopping criteria in CTP Section 3.3.4.1 and CTP Appendix 10.2.
- **Ketoacidosis**: If metabolic acidosis, ketoacidosis, or diabetic ketoacidosis (DKA) is suspected further investigations should be done according to medical judgement and the clinical course until a diagnosis is made and/or the patient is recovered.

More details refer to CTP Section 5.2.6.1.4.

An independent Adjudication Committee will adjudicate certain hepatic events for the severity and causal relationship with the trial medication. Adjudication assessments will be incorporated to the database. Frequency tables will be provided for the PTs in the specified SMQs of events and for the adjudication endpoints. Tables will be provided for events qualifying for adjudication and then separately the events that were confirmed or non-assessable.

#### 7.8.2.5 User-defined adverse event category (UDAEC)

UDAEC will be summarized by dose group, primary system organ class and preferred term. In summary, [Table 7.8.2.5:1](#) provides the definition of UDAECs according to AE category or Standardized MedDRA Query (SMQ).

Table 7.8.2.5: 1      Definition of continuous UDAEC

Category	Safety topic	Definition
UDAEC	Hypotension	Investigator-reported, as a dedicated AE category on the AE eCRF page
UDAEC	Syncope	Investigator-reported, as a dedicated AE category on the AE eCRF page
UDAEC	Acute kidney injury	SMQ ‘Acute renal failure’, narrow scope
UDAEC	Peripheral edema	SMQ ‘Haemodynamic oedema, effusions and fluid overload’
UDAEC	Bleeding	SMQ ‘Haemorrhages’, narrow scope
UDAE	Liver events	Narrow sub-SMQ ‘Liver related investigations, signs, and symptoms’, narrow sub-SMQ ‘Cholestasis and jaundice of hepatic origin’, narrow sub-SMQ ‘Hepatitis, non-infectious’

Category	Safety topic	Definition
		and narrow sub-SMQ 'Hepatic failure, fibrosis and cirrhosis and other liver damage-related conditions'

Summary of hypotension and syncope will be presented for both patient-based and event-based analyses. ae

Analysis on hypotension based on baseline BP and the lowest BP during the episode will be carried out. Criteria for significant (vs. non-significant) hypotensive episode are:

- Baseline SBP  $\leq 140$ : decrease  $\left( \frac{\text{lowest SBP during the episode} - \text{baseline SBP}}{\text{baseline SBP}} \right) \geq 30\%$ ;
- Baseline SBP  $> 140$ : decrease  $\left( \frac{\text{lowest SBP during the episode} - \text{baseline SBP}}{\text{baseline SBP}} \right) \geq 40\%$ ;
- Or lowest SBP during the episode  $< 90$ .
- Baseline DBP  $\leq 70$ :  $\left( \frac{\text{lowest DBP during the episode} - \text{baseline DBP}}{\text{baseline DBP}} \right) \geq 30\%$ ;
- Baseline DBP  $> 70$ :  $\left( \frac{\text{lowest DBP during the episode} - \text{baseline DBP}}{\text{baseline DBP}} \right) \geq 40\%$ ;
- Or lowest DBP during the episode  $< 50$ .
- Lowest mean arterial pressure (MAP=DBP+1/3(SBP-DBP)) during the episode  $< 70$ .

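### The SAP's relative blood-pressure criteria for a significant hypotensive episode subtract in the wrong order, so no fall can meet them and only the absolute limits work

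*SAP*

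**What the plan says.** SAP section 7.8.2.5 announces a separate look at hypotension: "Analysis on hypotension based on baseline BP and the lowest BP during the episode will be carried out". The list that follows is headed "Criteria for significant (vs. non-significant) hypotensive episode are" and has two kinds of criterion.

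- **Relative criteria (four lines).** Each starts from the lowest value ("lowest DBP during the episode" in the diastolic lines), subtracts baseline and divides by baseline. For SBP the result must be at least 30% when baseline is 140 or less, and at least 40% when it is above 140. For DBP the limits are the same, with the split at a baseline of 70. The word *decrease* stands before the bracket in the two SBP lines and is absent from the two DBP lines.
- **Absolute criteria (three lines).** "Or lowest SBP during the episode" below 90; "Or lowest DBP during the episode" below 50; and "Lowest mean arterial pressure (MAP=DBP+1/3(SBP-DBP)) during the episode" below 70.

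Neither the SAP nor the protocol restates or corrects the relative formula elsewhere.

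**The concern.** A criterion for a fall in pressure has to be one that a fall can satisfy. Lowest minus baseline is negative whenever pressure drops, so it cannot reach a positive limit. A program written from the four lines as printed would leave the relative half of the definition inactive. In the DBP lines, where no word gives the direction, it would respond only to rises.

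This matters because hypotension is the main mechanism-related risk of the drug. The protocol calls orthostatic dysregulation dose-limiting (sections 3.2 and 4.1.2) and puts hypotension first among the risks in Table 1.4.2:1. With about 20 patients per group (protocol synopsis), one or two episodes moved from significant to non-significant would show in the table. The error runs toward under-counting.

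**Working it through.** The plan gives no worked figure to reproduce, so the check evaluates the printed rule directly. All inputs come from SAP 7.8.2.5. Write B for baseline and L for the lowest value in the episode. The printed ratio is r = (L − B)/B, with limits of +30% or +40%.

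**1. Sign.** If L < B then r < 0, so r ≥ +30% is impossible for a fall. This was confirmed on a grid of integer baselines (SBP 80–220, DBP 40–130) and lowest values (20–260). The printed ratio flagged 0 of 18,330 SBP falls and 0 of 5,915 DBP falls.

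**2. What the DBP lines select when read literally.**
- 65 to 85: (85 − 65)/65 = +30.8%, flagged at the 30% limit.
- 80 to 112: (112 − 80)/80 = +40.0%, flagged at the 40% limit.
- 90 to 53: (53 − 90)/90 = −41.1%, not flagged.

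**3. Where the absolute limit on the same pressure does not cover the intended rule.** The intended rule is L ≤ 0.7B (30% fall) or L ≤ 0.6B (40% fall). It adds something only if such an L can still be at or above the absolute limit.

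| Band | Condition | Baseline needed |
|---|---|---|
| SBP, B ≤ 140 | 0.7B ≥ 90 | B ≥ 128.6, so about 129–140 |
| SBP, B > 140 | 0.6B ≥ 90 | B ≥ 150 |
| DBP, B ≤ 70 | 0.7B ≥ 50 | B ≥ 71.4, outside the band: never |
| DBP, B > 70 | 0.6B ≥ 50 | B ≥ 83.3 |

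For baseline DBP of 70 or less, a 30% fall gives at most 0.7 × 70 = 49. The limit of DBP below 50 already catches it, so that relative line adds nothing.

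**4. The MAP limit narrows this further.** MAP = DBP + (SBP − DBP)/3, so MAP ≥ 70 means 2 × DBP + SBP ≥ 210.
- Lowest SBP of 90 needs DBP of at least 60; lowest SBP of 98 (0.7 × 140) needs at least 56.
- Lowest DBP of 50 needs SBP of at least 110; lowest DBP of 54 (0.6 × 90) needs at least 102.

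The baseline ranges in step 3 are therefore necessary but not sufficient.

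**5. Episodes that only a relative rule would catch.**

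| Episode | SBP fall | DBP fall | Lowest MAP | Intended rule met | Flagged as printed |
|---|---|---|---|---|---|
| 150/90 to 110/53 | 40/150 = 26.7% (limit 40%) | 37/90 = 41.1% (limit 40%) | 53 + 57/3 = 72 | DBP | No |
| 140/90 to 95/60 | 45/140 = 32.1% (limit 30%) | 30/90 = 33.3% (limit 40%) | 60 + 35/3 = 71.7 | SBP | No |

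In both, SBP is not below 90, DBP is not below 50 and MAP is not below 70.

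**6. After reversing the subtraction.** With (B − L)/B, DBP 90 to 53 gives +41.1% and SBP 140 to 95 gives +32.1%; both are flagged. DBP 65 to 85 gives −30.8% and is not.

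**The case against.** The strongest reply is that the intent is evident. The list defines hypotensive episodes, and in the SBP lines *decrease* gives the direction while the percentage gives the size. A careful programmer would probably code those two lines correctly. That stands for SBP, and it weakens the second example above. It does not stand for DBP, where no such word appears and two programmers could differ. It is also possible that absolute-value bars were lost from the text copy of the formula. The same form on all four lines makes this unlikely, and an absolute value would still flag rises.

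A reader might infer three stronger things that the documents do not support.

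- *That the section flags no fall in pressure at all.* It does flag falls: the SBP, DBP and MAP limits are written in the right direction.
- *That diastolic rises would fill the table.* A false flag needs even the lowest DBP of a hypotensive episode to be at least 30% above baseline. The hypotension category in the same section is investigator-reported, so this should be rare.
- *That a trial endpoint is affected.* The secondary endpoints on hypotension and syncope (protocol 2.1.3, SAP 5.2) rest on investigator-judged CTCAE grade and on discontinuation. SAP 7.8.3 separately reports blood-pressure changes and minimum values, and protocol 7.1 plans no testing.

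**Conclusion.** Wrong as written, with limited reach. All four relative criteria contradict their purpose; the two diastolic lines are the more serious because nothing in them signals the intended direction. The practical effect is possible under-counting of significant episodes in a descriptive safety table. It is confined to episodes that meet a relative rule alone: baseline SBP of about 129–140 or at least 150, or baseline DBP of about 83.3 or more, with lowest MAP at least 70. The documents do not allow the number of such episodes to be predicted.

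This rests on two assumptions. One is that meeting any single criterion is enough, which the list suggests but does not state for the set as a whole. The other is that the lowest SBP and DBP in the examples come from the same reading. The sign error itself depends on neither.

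**What to change.** In SAP 7.8.2.5, write all four relative criteria as (baseline − lowest)/baseline, and add *decrease* to the two DBP lines so that they match the SBP lines. Leave every threshold as it is. Two cases would serve as a programming check: 150/90 to 110/53 must be flagged, and a DBP going from 65 to 85 must not be flagged by the relative line. The cost is one SAP edit. It needs no new data, alters no clinical rule and has no downside.

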#### **1.4.2 Risks**

Trial participants will be exposed to trial-related risks due to exposure to the investigational medicinal product (BI 685509), the investigational medicinal product empagliflozin, the trial procedures and other risks. For details refer to Tables [1.4.2: 1](#), [1.4.2: 2](#), [1.4.2: 3](#) and [1.4.2:4](#) below

Table 1.4.2:1                    Overview of trial related risks - investigational medicinal product (BI 685509)

Possible / known risks of clinical relevance	Summary of data, rationale for the risk	Mitigation strategy
Potential AEs such as hypotension / orthostatic dysregulation, tachycardia, peripheral oedema and gastrointestinal events such as diarrhoea, abdominal pain and nausea	Primarily related to the vasodilatory effects and subsequent reactions or gastrointestinal effects which are directly related to the mechanism of action	To minimise the risk of severe or serious side effects, participants of this trial will only be exposed to doses that have been safely administered to healthy volunteers and patients in the preceding trials (refer to the IB [ c02778238 ] and Sections 1.2.1 and 4.1.2 ). All patients will be monitored for AEs, and BP and HR will be measured daily (by the patient at home) during the treatment period. Patients with oedema or gastrointestinal side effects will be managed by standard of care, and patients with a known history of orthostatic dysregulation and those with a SBP < 100 mmHg and a DBP < 70 mmHg will be excluded. In addition, up-titration to the maintenance dose within each treatment group will occur at weekly intervals in order to increase the tolerability of the trial medication with regards to cardiovascular effects.
Potential QT-interval prolongation	Refer to Section 1.2.1	Patients with long QT / QTcF-interval, patients with a family history of long QT syndrome, or those using concomitant therapies known to increase the risk of Torsade de Points

**Table 1.4.2:1** Overview of trial related risks - investigational medicinal product (BI 685509) (cont)

Possible / known risks of clinical relevance	Summary of data, rationale for the risk	Mitigation strategy

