Following enrolment / randomisation, the trial design includes a dose-titration period. The mechanism related vasodilatation of BI 685509 can lead to orthostatic dysregulation and hypotensive episodes (refer to [Table 1.4.2: 1](#)). The orthostatic dysregulation is dose-limiting and clinical tolerability is improved if the dose is titrated. A *BID* administration also allows the total daily exposure of BI 685509 to be further increased while high peak concentrations are avoided. Hence, in this trial, a dose-titration regimen of [REDACTED] *BID* to [REDACTED] *BID* to [REDACTED] *BID* will be followed.

Patients selected for this trial have a risk for further progression into decompensation, a severe outcome. A DMC, independent from the Sponsor, will therefore be established to review safety data at intervals to identify any potential risks and / or the need for implementation of further safety measures. The tasks and responsibilities of the DMC members will be detailed in the DMC charter (refer to [Section 8.7](#)).

An independent AC will also be established for adjudication of hepatic injury. The tasks and responsibilities of the AC members will be detailed in the AC charter (refer to [Section 8.7](#)).

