## **11. HISTORY TABLE**

Table 11: 1 History table

Version	Date (DD-MMM- YY)	Author	Sections changed	Brief description of change
1.0	20-JUN-24	[REDACTED]	None	This is the final TSAP.

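### SAP 7.8.2.5: the two diastolic relative-change lines for a significant hypotensive episode have the wrong sign, so as printed only a rise in diastolic pressure meets them

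*SAP*

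**What the plan says.** SAP 7.8.2.5 announces the analysis: "Analysis on hypotension based on baseline BP and the lowest BP during the episode will be carried out". The list, introduced by "Criteria for significant (vs. non-significant) hypotensive episode are", has three parts.

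- **SBP.** A *decrease*, with ratio (lowest − baseline)/baseline, of at least 30% if baseline SBP is 140 or below, or at least 40% if it is above 140. The alternative, opening "Or lowest SBP during the episode", is a value under 90.
- **DBP.** The same form of ratio, without the word *decrease*, of at least 30% if baseline DBP is 70 or below, or at least 40% if it is above 70. The alternative, opening "Or lowest DBP during the episode", is a value under 50.
- **MAP.** "Lowest mean arterial pressure (MAP=DBP+1/3(SBP-DBP)) during the episode" under 70.

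The two occurrences of *Or* link lines inside the SBP part and inside the DBP part. No word links the three parts, and the lead-in does not say whether one or all must hold. No other visible section of the protocol or SAP restates the rule. The SAP history table records for version 1.0: "This is the final TSAP".

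**The concern.** A rule meant to identify large falls in pressure contains two lines that a fall cannot meet. Hypotension matters for this drug. Protocol 3.2 says: "The orthostatic dysregulation is dose-limiting and clinical tolerability is improved if the dose is titrated". This list is also the only numeric blood-pressure grading of hypotensive episodes in the visible SAP. If the DBP lines are coded as printed, some deep diastolic falls are graded non-significant, and an episode in which DBP rose could be graded significant. The missing connector between the three parts leaves a second choice to whoever programs the table.

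**Working it through.** The SAP gives no figure for this rule, so there is none to reproduce. The thresholds below come from SAP 7.8.2.5. The blood pressures in the examples are illustrative.

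**1. Direction of the DBP lines.** (lowest − baseline)/baseline ≥ 0.30 means lowest ≥ 1.30 × baseline; ≥ 0.40 means lowest ≥ 1.40 × baseline. For integer baselines from 50 to 110 and every lower value down to 30, no fall met either line. A rise did: 60 to 78 is (78 − 60)/60 = +30%.

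**2. Where the slip can matter.** Read the lines as falls and ask what they add to DBP < 50.

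- 30% line, baseline at most 70: lowest ≤ 0.70 × 70 = 49, already under 50. It adds nothing.
- 40% line, baseline above 70: 0.60 × 83 = 49.8, already under 50; 0.60 × 84 = 50.4. It adds something only from a baseline of 84 upward.

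So the DBP part misses falls of 40% or more from a baseline of 84 or above that stop at 50 or higher. The MAP line catches many of these. MAP = (SBP + 2 × DBP)/3, so MAP ≥ 70 needs SBP ≥ 210 − 2 × DBP: at least 110 when DBP is 50, and at least 100 when DBP is 55.

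**3. An episode that meets no printed criterion.** Baseline 150/95, lowest 100/55:

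| Criterion | Value | Met as printed? |
|---|---|---|
| SBP fall ≥ 40% (baseline > 140) | 50/150 = 33.3% | No |
| SBP < 90 | 100 | No |
| DBP ratio ≥ 40% (baseline > 70) | (55 − 95)/95 = −42.1% | No |
| DBP < 50 | 55 | No |
| MAP < 70 | 55 + 45/3 = 70.0 | No |

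With the sign corrected, the DBP line is met (42.1% ≥ 40%). The episode is then significant if one criterion suffices, and still non-significant if all three parts are needed.

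**4. How often.** The documents give no blood-pressure distribution, so this step rests on assumptions: mean baseline 120/72, 125/75 or 132/80 (SD 14/9); mean fall 20/10, 30/16 or 40/24 (SD 10/7); SBP–DBP correlation 0.3, 0.6 or 0.8. That makes 27 settings, each with 300,000 to 400,000 simulated episodes. Correcting the sign changed the share graded significant by at most 0.2 percentage points if one criterion suffices, and by at most about 0.6 points if all three are required.

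**5. One or all.** Suppose all three parts were required. With baseline SBP at most 140, meeting the SBP part means lowest SBP ≤ 0.70 × 140 = 98. With DBP at most 49, MAP ≤ 49 + (98 − 49)/3 = 65.3, so MAP < 70 follows automatically. At these SBP baselines the MAP line could affect a grade only from a baseline DBP of 94: a 40% fall allows 56 (0.60 × 94 = 56.4), and 56 + (98 − 56)/3 = 70.0. In the same 27 settings it changed the all-three grade in fewer than ten episodes per setting. If one criterion suffices, MAP alone decides roughly 2.5% to 8.6% of episodes.

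**The case against.** The strongest reply is that nobody would code a rise in diastolic pressure as hypotension. The section is about hypotensive episodes, the parallel SBP lines say *decrease*, and an analyst would supply the word. That is probably so, and it is why the expected effect is small. The printed rule is still wrong, though, and no other section corrects it.

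A second reply is that little depends on the table. This stands. Hypotension is investigator-reported, and the secondary endpoints use CTCAE grade 3 or higher and treatment discontinuation. Adverse events are also tabulated by maximum CTCAE grade, and vital-sign minima are summarised separately. No hypothesis is tested.

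A reader might go further and infer that the missing connector makes the count of significant episodes highly uncertain. Across the 27 assumed settings, requiring one criterion or all three gives shares that differ by 12 to 50 percentage points. The documents do not support presenting that as realistic reporting uncertainty. Requiring all three makes the separate MAP line nearly pointless, so one criterion is the sensible reading and the one an analyst would likely adopt. The gap also rests on assumed pressures with fixed SDs. The simulation applies the blood-pressure exclusion to baseline, whereas the protocol applies it at Visit 1a. With 80 planned patients and no expected number of episodes, the gap cannot be turned into a count.

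Nor do the SBP lines share the error: their ratio is also negative for a fall, but *decrease* gives its direction.

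**Conclusion.** The two DBP relative-change lines are wrong as written. That follows from the text alone. Which falls escape the DBP part also follows by arithmetic: 40% or more, from a baseline of about 84 or higher, ending at 50 or above. Such an episode escapes the whole rule only if neither the SBP part nor MAP < 70 catches it, as in the 150/95 example. The 30% line costs nothing in missed falls, because DBP < 50 already covers it.

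The practical effect is small. The figure of at most about 0.6 percentage points depends on the assumed distributions. The consequence is confined to a descriptive safety table; no efficacy result or secondary endpoint depends on it. The absent one-or-all statement is a real gap in the text, but one with a sensible reading. It is worth closing in the same edit.

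**What to change.** Replace the list in SAP 7.8.2.5 with:

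An episode is significant if at least one of the following holds:

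1. (baseline SBP − lowest SBP)/baseline SBP is ≥ 30% if baseline SBP ≤ 140, or ≥ 40% if baseline SBP > 140; or lowest SBP < 90.
2. (baseline DBP − lowest DBP)/baseline DBP is ≥ 30% if baseline DBP ≤ 70, or ≥ 40% if baseline DBP > 70; or lowest DBP < 50.
3. Lowest MAP < 70.

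If the sponsor does intend all three to be required, the lead-in should say so. The cost is a sign correction and one sentence, with no new data and no new table. Dropping the redundant DBP 30% line, or adding a count for each criterion, is optional.

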### **7.8.3 Vital signs**

The analyses of vital signs (blood pressure and pulse rate) will be descriptive in nature. Descriptive statistics of vital signs over time during treatment period and post-treatment period (pre-dose, 1 hour and 2 hour) and for the difference from baseline and pre-dose will be provided by treatment, including the last value, the minimum value, and the maximum value within the study period as described in [Table 6.1:1](#). Figures for change from baseline and change from pre-dose for on-treatment visit and post-treatment visit will be provided as well.

### **7.8.4 ECG**

Abnormal findings in 12-lead ECG will be reported as baseline conditions (at screening) or as AEs (during the trial) if judged clinically relevant by the investigator and will be analysed as such.

No separate listing or analysis of ECG data will be prepared.

## **7.9 OTHER ANALYSIS**

### **7.9.1 Ultrasound**

[figure not shown]
Descriptive analysis of change from baseline of portal vein diameter at week 8 will be provided. A listing of all the collected data from the ultrasound CRF page for each patient will be provided.

**Boehringer Ingelheim  
TRIAL STATISTICAL ANALYSIS PLAN  
1366-0029**

**Page 31 of 35**

**c44538732-01**

Proprietary confidential information © 2024 Boehringer Ingelheim International GmbH or one or more of its affiliated companies.

**8. TIMEPOINT OF RELEASE OF TREATMENT  
INFORMATION**

Not applicable as no blinding procedure is needed.

## **11. HISTORY TABLE**

Table 11: 1 History table

Version	Date (DD-MMM- YY)	Author	Sections changed	Brief description of change
1.0	20-JUN-24	[REDACTED]	None	This is the final TSAP.
